5.1 Imputation rules

5.1.1 Study drug

The following rule will be used for the imputation of date of last administration for a given study treatment component.

Case 1: The date of last administration is completely missing, and the EOT visit date is complete, then this latter date should be used.

Case 2: Only Year (yyyy) of the dose end date is available and yyyy < the year of EOT date:

Impute date= Dec31yyyy

Case 3: Only Year (yyyy) of the dose end date is available and yyyy = the year of EOT date:

Impute date=EOT date

Case 4: Both Year (yyyy) and Month (mm) is available for the date of last administration, and yyyy = the year of EOT date and mm < the month of EOT visit:

Impute date= last day of the Month (mm).

After imputation, compare the imputed date with the start date of that specific record, if the imputed date is < start date of that record

Impute date= the start date of that record.

Subjects with missing start dates are to be considered missing and no imputation will be made. If the date of first administration is missing, then the date of last administration should not be imputed.

5.1.2 AE date imputation

Date imputation is the creation of a new, complete date from a partial one according to an agreed and acceptable algorithm. Missing date for AE will be handled according to STL standard.

A partial date is simply an incomplete date e.g., ddOCT2001 the days are missing from this DDMMYYYY date.

Partial adverse event start dates, if left partial, would ultimately mean the following

- It would not be possible to place the adverse event in time.
- Therefore the treatment/dosage at the time of the event would be unknown.
- Therefore the event could not be reported/summarized appropriately - if at all.

There **will be no** attempt to impute the following

- **Missing** AE start dates
- AE start dates missing the year
- Partial/missing AE **end dates**

Table 5-1 AE/treatment date abbreviations

	Day	Month	Year
Partial AE start date	<not used>	AEM	AEY
Treatment start date (TRTSTD)	<not used>	TRTM	TRTY

The following matrix [Table 5-2](#) describes the possible combinations and their associated imputations. In the boxes the upper text indicates the imputation and the lower text the relationship of the AE start date to the treatment start date (TRTSTD).

Table 5-2 AE partial date imputation algorithm

AEM Missing		AEM < TRTM	AEM = TRTM	AEM > TRTM
AEY Missing	NC Uncertain	NC Uncertain	NC Uncertain	NC Uncertain
AEY <	(D)	(C)	(C)	(C)
TRTY	Before TRTSTD	Before TRTSTD	Before TRTSTD	Before TRTSTD
AEY =	(B)	(C)	(B)	(A)
TRTY	Uncertain	Before TRTSTD	Uncertain	After TRTSTD

AEY > TRY	(E) After TRTSTD	(A) After TRTSTD	(A) After TRTSTD	(A) After TRTSTD
--------------	---------------------	---------------------	---------------------	---------------------

Table 5-3 AE/treatment date relationship and imputation

Relationship	
Before TRTSTD	Indicates AE start date prior to Treatment Start Date
After TRTSTD	Indicates AE start date after Treatment Start Date
Uncertain	Insufficient to determine the relationship of AE start date to Treatment Start Date
Imputation Calculation	
NC/Blank	No convention/imputation
(A)	01MONYYYY
(B)	TRTSTD+1
(C)	15MONYYYY
(D)	01JULYYYY
(E)	01JANYYYY

The following [Table 5-4](#) gives a few examples.

Table 5-4 Example Scenarios

Partial AE start date	Treatment start date	Relationship	Imputation calculation	Imputed date
12mmYYYY	20OCT2001	Uncertain	NC	<blank>
ddmmm2000	20OCT2001	Before	(D)	01JUL2000
ddmmm2002	20OCT2001	After	(E)	01JAN2002
ddmmm2001	20OCT2001	Uncertain	(B)	21OCT2001
ddSEP2001	20OCT2001	Before	(C)	15SEP2001
ddOCT2001	20OCT2001	Uncertain	(B)	21OCT2001
ddNOV2001	20OCT2001	After	(A)	01NOV2001

5.1.3 Concomitant medication date imputation

The imputation of the start date of concomitant medication will follow the same convention for AE date. Partial concomitant medication end date will not be imputed.

5.1.3.1 Prior therapies date imputation

Start date:

The same rule which is applied to the imputation of AE/concomitant medication start date will be used with the exception that for scenario (B) will be replaced to be 'start date of study drug -1'.

End date:

Imputed date = min (start date of study drug, last day of the month), if day is missing; Imputed date = min (start date of study drug, 31DEC), if month and day are missing.

If the end date is not missing and the imputed start date is after the end date, use the end date as the imputed start date.

If both the start date and the end date are imputed and if the imputed start date is after the imputed end date, use the imputed end date as the imputation for the start date.

5.1.3.2 Other imputations

Incomplete date for death

All dates must be completed with day, month and year.

If the day or month is missing, death will be imputed to the maximum of the last contact date (excluding the date of death) and the following:

- Missing day: 15th of the month and year of death
- Missing day and month: July 1st of the year of death

5.2 Creatinine clearance recalculation

The recalculated creatinine clearance will be calculated using the Schwartz formula (pediatric population at baseline). The MDRD derivation will be provided in the derived datasets only for possible future requests.

In the formulae below, CrCl denotes Creatinine Clearance, SCr denotes Serum Creatinine in $\mu\text{mol/L}$; age in years is calculated from date of birth and date of the relevant blood sample. Weight and height are the last available measurements at the time of the relevant blood sample.

Schwartz formula (<18 years of age at beginning of the study),

CrCl (mL/min) = $(k \times \text{height}) / (\text{SCr} \times 0.01131)$ with
k = 0.45 for children <1 year based on current age
k = 0.55 for children from 1 to 12 years based on current age

eGFR (mL/min/1.73m²) =
 $186.3 \times (\text{SCr} \times 0.01131)^{-1.154} \times \text{age}^{-0.203} \times E \times S$ where,
E is ethnicity: E=1.212 if patient is black, else E=1
S is sex: S=0.742 if patient is female, else S=1

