7.1 Study flow and visit schedule

Table 7-1 lists all of the assessments and indicates with an “X”, the visits when they are performed. All data obtained from these assessments must be supported in the patient’s source documentation. All data obtained from these assessments and noted with an “S” in the category column must be supported in the patient’s source documentation. The “D” in the category column must be supported in Novartis eCRF database.

No CRF will be used as a source document.

[figure not shown]

Table 7-1 Visit evaluation schedule

	Category	Protocol Section	Screening Visit 1 Day -14 to -8	Screening Visit 2 Day -7 to -1 (Newly Initiated DFX patients)	Baseline								End of study treatment (EoT)	30 day safety follow-up	
Visit Name			SV1	SV2*	Week 1 Day 1	Week 2 ± 3 days	Week 3 ± 3 days	Week 4 ± 3 days	Week 8 ± 7 days	Week 12 ± 7 days	Week 16 ± 7 days	Week 20 ± 7 days			
Obtain Informed Consent	D	11.3	X												
IRT(IWRS)	S	7.1.2.1	X	X	X	X	X	X	X	X	X	X			
Patient History															
Demography	D	7.1.2.3	X												
Inclusion/exclusion criteria	D	5.2, 5.3	X	X											
Medical History	D	7.1.2.3	X												
Transfusion Therapy ¹	D	6.4	X	Continuous – up to 30 days after last dose											
Prior and Concomitant Medications/Prior Chelation	D	6.4	X	Continuous – up to 30 days after last dose											
Surgical and Medical Procedures	D	6.4	X	Continuous – up to 30 days after last dose											
Physical Examination															
Physical Examination	S	7.2.2.1	X	X	X	X	X	X	X	X	X	X	X		
Height	D	7.2.2.3	X												X
Weight	D	7.2.2.3	X	X	X			X	X	X	X	X			X
Vital signs	D	7.2.2.2	X	X	X	X	X	X	X	X	X	X			X

Visit Name	Category	Protocol Section	Screening Visit 1	Screening Visit 2 Day -7 to -1 (Newly Initiated DFX patients)	Week 1 Day 1								End of study treatment (EoT) Week 24 ± 7 days	30 day safety follow-up	
			Day -14 to -8			Baseline	Week 2 ± 3 days	Week 3 ± 3 days	Week 4 ± 3 days	Week 8 ± 7 days	Week 12 ± 7 days	Week 16 ± 7 days	Week 20 ± 7 days		
mSICT	D	7.2.8	X ³				X		X					X	
Palatability questionnaire	D	7.2.8	X ³				X		X		X			X	
GI symptom questionnaire	D	7.2.8	X ³			X	X	X	X	X	X	X	X	X	
Study drug dispensation	D	6.3.1				X			X	X	X	X	X		
End of phase disposition	D			X	X									X	
Safety follow-up	D	4.1													X

* SV2 is applicable only to patients who are chelation naïve or are currently treated with chelation therapy other than deferasirox. Patients on prior deferasirox will NOT be subject to SV2

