7.2.2.3 Height and weight

Standing height will be assessed at screening visit 1 and end of treatment. Weight will be assessed at screening visits 1 and 2, week 1/day 1, monthly visits, week 4 through week 20 and end of treatment as detailed in [Table 7-1](#).

Height in centimeters (cm) and body weight (to the nearest 0.1 kilogram [kg] in indoor clothing, but without shoes) will be measured.

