7.2.2.5.2 Clinical chemistry

Clinical chemistry samples will be collected at screening visit 1 and screening visit 2 and at visits as detailed in [Table 7-1](#).

The parameters to be measured at screening visits and at specific timepoints in the study are as follows:

Screening Visit 1 -All patients:

Parameters to be measured include serum creatinine, creatinine clearance, blood urea nitrogen or urea, total bilirubin, direct bilirubin, ALT, AST, alkaline phosphatase, uric acid, total protein, bicarbonate, albumin, chloride, glucose, inorganic phosphate, potassium, sodium, calcium, magnesium and serum ferritin.

Screening Visit 2_- (Only patients who are chelation naïve or treated with iron chelation other than deferasirox):

Parameters to be measured include serum creatinine, creatinine clearance and serum ferritin.

Study Visit Baseline (Week 1) – All patients:

Parameters to be measured include serum creatinine, creatinine clearance, blood urea nitrogen or urea, total bilirubin, direct bilirubin, ALT, AST, alkaline phosphatase uric acid, total protein, bicarbonate, albumin, chloride, glucose, inorganic phosphate, potassium, sodium, calcium, magnesium and serum ferritin.

Study Visit Week 2 – All patients:

Parameters to be measured include serum creatinine and creatinine clearance

Study Visit Week 3 – All patients:

Parameters to be measured include serum creatinine, creatinine clearance, total bilirubin, direct bilirubin, ALT, AST, uric acid, total protein, bicarbonate, albumin, chloride, glucose, inorganic phosphate, potassium, sodium, calcium, magnesium and alkaline phosphatase.

Study Visit Weeks 4, 8, 12, 16, 20 and end of treatment – All patients:

Parameters to be measured include serum creatinine, creatinine clearance, blood urea nitrogen or urea, total bilirubin, direct bilirubin, ALT, AST, alkaline phosphatase, uric acid, total protein, bicarbonate, albumin, chloride, glucose, inorganic phosphate, potassium, sodium, calcium, magnesium and serum ferritin.

Renal parameters are monitored weekly to establish a reliable pretreatment baseline and hepatic parameters are monitored biweekly for safety at the initiation of treatment.

For calculated CrCl from local labs where the enzymatic method is used to determine creatinine clearance the modified Schwartz formula will be used for analysis. This estimate will be provided each time serum creatinine is collected.

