2.10.2 Statistical hypothesis, model, and method of analysis

A summary table will be provided for the change in SF from baseline for each visit up-to 24 weeks of treatment using FAS. A listing will also be provided including current SF level, change from baseline by visit and by patient. A graphical representation of SF change from baseline by box-plot will be provided for each visit using FAS.

For the summary table, all scheduled and unscheduled visits will be considered. If a scheduled visit does not occur, then an unscheduled visit will be mapped to a scheduled visit by the below rule:

- The target date of a scheduled visit will be defined relative to Day 1 as $(X-1)*7+1$, where X is the number of weeks, such as X=1, 2, ... For example, the target day for Week 12 visit will be $(12-1)*7+1 = 78$ days.
- Unscheduled visit then will be mapped to a scheduled visit by:
 - Weeks 2 and 3: -1 day / +1 day
 - Week 4 : -1 day/+7 days
 - Week 8,12,16, 20 and 24 (EOT): -7 days / +7 days

If a scheduled visit already exists, then no unscheduled visit will be mapped against a scheduled visit. If no scheduled visits exist, the unscheduled visit which is the closest to the target scheduled visit will be considered. If two unscheduled visits are equidistant from the targeted scheduled visit then prior to the targeted scheduled visit will be consider as scheduled visit. After mapping unscheduled visit to a scheduled visit, only scheduled visit will be considered for the summary level outputs.

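### Creatinine clearance at end of treatment uses a newer height than every earlier visit, so its change from baseline is not comparable with Weeks 2 to 20

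*SAP*

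**What the plan says.** SAP section 5.2 recalculates CrCl as k × height / (SCr × 0.01131), with SCr in µmol/L. One constant covers the whole enrolled age range: "k = 0.55 for children from 1 to 12 years based on current age". The height to use is fixed by this sentence: "Weight and height are the last available measurements at the time of the relevant blood sample".

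Protocol section 7.2.2.3 sets the height schedule: "Standing height will be assessed at screening visit 1 and end of treatment". The Height row of Table 7-1 likewise has two marks. Weight, which does not enter the Schwartz formula, is taken far more often: "Weight will be assessed at screening visits 1 and 2, week 1/day 1, monthly visits, week 4 through week 20 and end of treatment".

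CrCl is needed much more often than height is measured. Protocol section 7.2.2.5.2 says of the estimate: "This estimate will be provided each time serum creatinine is collected". Creatinine is sampled at screening, at Weeks 1, 2 and 3, and then at "Study Visit Weeks 4, 8, 12, 16, 20 and end of treatment".

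CrCl change from baseline over time is part of the secondary overall-safety endpoint (protocol Table 3-1, SAP Table 1-1). SAP section 2.11 presents it as box plots for each visit, and section 2.11.4 adds descriptive summaries. Neither document has an interpolation rule, a sensitivity analysis or a stated limitation on the age of the height.

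**The concern.** The patients are 2 to 5 years old and will grow during six months on study. CrCl is directly proportional to height, so the age of the height measurement passes straight into the result. On the planned schedule baseline and Weeks 2 to 20 share one height, and EoT is the first visit with a new one. The by-visit display therefore joins values that contain no growth to a last value that contains about 25 weeks of it.

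The error has the same sign in every growing child, so averaging over about 40 patients does not remove it. A reader of the box plots could take the EoT step for a change in renal function, or could miss a small real decline that the step offsets.

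**Working it through.** The plan gives no figure for this effect, so there is none to reproduce.

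**Inputs from the documents**
- Formula and k = 0.55: SAP 5.2.
- Timing of SV1: "Screening Visit 1 Day -14 to -8" (protocol Table 7-1). Day -14 is used here.
- Visit days, SAP 2.10.2: "The target date of a scheduled visit will be defined relative to Day 1 as" (X-1)*7+1. Week 20 is 19 × 7 + 1 = Day 134, and Week 24 (EoT) is 23 × 7 + 1 = Day 162.
- Age of the SV1 height: 133 + 14 = 147 days (21 weeks) at Week 20, and 161 + 14 = 175 days (25 weeks) at Week 24.
- Baseline, SAP 2.1.2.6: last assessment on or before the start of treatment. On the planned schedule it uses the SV1 height.

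**Assumptions (not in the documents)**
- Growth of 4 to 9 cm/year and SV1 height of 85 to 115 cm, with 7 cm/year and 95 cm as the central case.

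**Formulas**
- Height at a visit = H(SV1) + rate × days / 365.25.
- Shortfall against CrCl on current height = H(SV1) / H(visit) − 1.
- Step at EoT with constant creatinine = H(EoT) / H(SV1) − 1.

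**Central case**
- Week 20 height = 95 + 7 × 147/365.25 = 97.82 cm. Shortfall = 95/97.82 − 1 = −2.9%.
- EoT height = 95 + 7 × 175/365.25 = 98.35 cm. Step = 98.35/95 − 1 = +3.5%.

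| SV1 height, growth | Day 1 | Week 4 | Week 12 | Week 20 | Step at EoT |
|---|---|---|---|---|---|
| 115 cm, 4 cm/yr | −0.1% | −0.3% | −0.9% | −1.4% | +1.7% |
| 95 cm, 7 cm/yr | −0.3% | −0.7% | −1.8% | −2.9% | +3.5% |
| 85 cm, 9 cm/yr | −0.4% | −1.0% | −2.6% | −4.1% | +5.1% |

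With SV1 at Day -8 the height ages are 141 and 169 days, and the central case becomes −2.8% and +3.4%.

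**What the reported series looks like (central case)**
1. Creatinine constant at 46.2 µmol/L. Reported CrCl is 0.55 × 95 / (46.2 × 0.01131) = 100.0 mL/min from Day 1 to Week 20, then 103.5 at EoT. On current height, Week 20 would be 103.0 and EoT 103.5. The reported series is flat and then steps; it does not decline.
2. Creatinine rising in proportion to height, so that current-height CrCl stays at 100.0. Reported CrCl is 95/95.27 × 100 = 99.7 at Day 1, 95/97.82 × 100 = 97.1 at Week 20 and 100.0 at EoT. The change from baseline is −2.6 mL/min at Week 20 and +0.3 at EoT: an artificial fall and rebound.
3. Masking. Suppose current-height CrCl fell from 103.0 at Week 20 to 100.0 at EoT. Both visits would be reported as 100.0, so a real fall of 2.9% over that interval would not show.

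**With interpolated height and constant creatinine**, the Week 20 to EoT change is H(EoT)/H(Week 20) − 1, which is +0.3% (115 cm, 4 cm/yr) to +0.8% (85 cm, 9 cm/yr). Under the present rule the same interval shows +1.7% to +5.1%. Interpolation does not remove the effect of growth on CrCl; it spreads it over the visits at which it occurs.

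**The case against.** The strongest reply is that the effect is small, rests on an assumed growth rate, and sits in a descriptive summary of one laboratory parameter among seven. Serum creatinine, which does not depend on height, is also shown by visit with box plots and shift tables, so an EoT step in CrCl without a creatinine change could be recognised as a height effect. This stands as a limit on the harm. It does not make EoT comparable with the earlier visits, and it asks the reader to make a correction that the SAP could make.

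Extra heights at unscheduled visits would shrink or move the step, and so would an early EoT visit after discontinuation. Neither can be relied on. The percentages also assume that the modified Schwartz formula, which protocol 7.2.2.5.2 names for enzymatic assays but does not print, is proportional to height too.

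Three stronger readings are tempting but not supported:
- A reader might see the EoT step as imitating renal recovery once treatment ends. For completers EoT is the Week 24 visit at the close of the treatment course, with no scheduled off-drug interval before it.
- A reader might infer that the artefact resembles the signal the study was set up to find. The primary objective concerns selected gastrointestinal disorders; CrCl is secondary.
- A reader might infer that the old height pushes children below 90 mL/min during the study. SAP 5.2 governs the analysis value, and the SAP uses 90 only as a baseline category, where the height is normally about two weeks old or less. The protocol's entry limit is applied at screening, also with a recent height. The documents do not say which height sites use for on-study CrCl, so the SAP rule cannot be shown to drive that limit.

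**Conclusion.** The point holds as a comparability problem. On the planned schedule CrCl from baseline to Week 20 uses the SV1 height and EoT uses a height about 25 weeks newer, with nothing in either document to correct for it. The distortion is modest: about 1.4% to 4.1% low at Week 20 and a step of about 1.7% to 5.1% at EoT (central case −2.9% and +3.5%). These sizes rest on assumed growth of 4 to 9 cm/year, SV1 heights of 85 to 115 cm, SV1 at Day -14 and the SAP target days; the step also assumes constant creatinine. The direction needs only that the children grow.

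Whether the reported series is flat and then steps, or falls and rebounds, depends on how creatinine moves with growth, which the documents do not settle. The secondary by-visit CrCl summaries are affected; the primary endpoint is not.

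**What to change.** In SAP 5.2, replace the last-available height for the CrCl recalculation by linear interpolation by date between the SV1 and EoT heights, and carry the SV1 height forward only when no later height exists. Add a sensitivity summary of EoT CrCl computed with the SV1 height, which isolates the step. Both heights are already scheduled, so this costs one sentence and one extra summary, to be settled before database lock.

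For visits still to come, height can be recorded at the monthly visits where weight is already taken. That needs a line in an amendment and a short extra measurement.

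The downside is that interpolated values for earlier visits use a height measured later, so they differ from anything calculated during the study. Patients without an EoT height keep the shortfall, and their number should be reported beside the summary.

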5.3 Exclusion criteria

Patients eligible for this study must not meet **any** of the following criteria:

1. Patients that receive more than one iron chelator at the same time as current iron chelation treatment. (Patients who have received combination therapy in their medical history but are currently being treated with a single ICT agent are eligible.)
2. Patients continuing on deferoxamine or deferiprone in addition to study treatment. (Patients switching to or continuing on deferasirox are eligible).
3. Unresolved adverse events if the patient was previously treated with deferiprone or deferoxamine or deferasirox.

4. Significant proteinuria as indicated by a urinary protein/creatinine ratio $> 0.5 \text{ mg/mg}$ in a non-first void sample urine measured at screening visit 1.
5. Serum creatinine $>$ age adjusted ULN measured at any screening visit
6. Creatinine clearance below 90 mL/minute measured at any screening visit. Creatinine clearance using the Schwartz formula will be estimated from serum creatinine measured at each respective visit.
7. ALT and/or AST $> 2.5 \times \text{ULN}$ measured at screening visit 1.
8. Total bilirubin (TBIL) $> 1.5 \times \text{ULN}$ measured at screening visit 1.
9. Patients with significant impaired GI function or GI disease that may significantly alter the absorption of oral deferasirox FCT (e.g. ulcerative diseases, uncontrolled nausea, vomiting, diarrhea, malabsorption syndrome, or small bowel resection).
10. History of and/or laboratory evidence of active Hepatitis B or Hepatitis C (HBsAg in the absence of HBsAb OR HCV Ab positive with HCV RNA positive).
11. Liver disease with severity of Child-Pugh Class B or C.
12. History of hypersensitivity to any of the study drug or excipients.
13. Patients participating in another clinical trial or receiving an investigational drug.
14. Patients with a known history of HIV seropositivity.
15. Patients unwilling or unable to comply with the protocol.
16. History of malignancy of any organ system, treated or untreated, within the past 5 years whether or not there is evidence of local recurrence or metastases, with the exception of localized basal cell carcinoma of the skin.
17. Significant medical condition interfering with the ability to partake in this study (e.g. uncontrolled hypertension, unstable cardiac disease not controlled by standard medical therapy, systemic disease: cardiovascular, renal, hepatic, etc.).

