For calculated CrCl from local labs where Jaffe method is used we will use the Schwartz formula. This estimate will be provided each time serum creatinine is collected.

All clinical chemistry samples will be sent to local laboratories.

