10.5.3.3 Laboratory abnormalities

All laboratory values will be converted into SI units and the severity grade calculated using the low/normal/high classifications based on laboratory normal ranges and for selected parameters by notable/extended ranges.

The following summaries will be generated separately for chemistry, urinalysis assessments:

- Shift tables using normal/notable/extended ranges to compare baseline to the worst on-treatment value (where applicable)
- Listing of all laboratory data with values flagged to show the corresponding normal/notable/extended ranges

For selected lab assessments such as hematology parameters, observed values (and changes from baseline) will be summarized by descriptive statistics (n, mean, standard deviation, minimum, lower quartile, median, upper quartile, and maximum).

Creatinine clearance will be estimated using the (modified) Schwartz formula and the change from baseline will be provided.

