2.1 Data analysis general information

Data will be analyzed by Novartis Oncology Biostatistics and Statistical programming personnel according to the data analysis described in Section 10 of the ICL670F2429 protocol, which will be available in Appendix 16.1.1 of the Clinical Study Report (CSR). Important information is given in the following sections and details are provided. For the final analysis, SAS version 9.4 or later (upon availability) will be used. As specified in the protocol, the study will continue until last patient received last dose plus 30-days follow-up. This date will be considered as the cut-off date.

Data from all patients who signed the main study informed consent for study participation in centers that participate in this study will be used in the analysis; due to expected small size of enrollment at individual centers, no center effect will be assessed. Each analysis will use all data in the database up to the analysis cutoff date, determined prior to database lock.

All available data from all patients up to the cutoff date will be reported. Data collected after patients' withdrawal of informed consent for further participation in the study will not be reported (except for death date which might be obtained from public records).

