Urinary total protein/creatinine ratio	>1.0 mg/mg at two consecutive measurements at least 7 days apart
Total bilirubin	$>2 \times ULN$
Direct bilirubin	$>2 \times ULN$

Summaries for the change from baseline will be provided for all parameters. Creatinine clearance will be estimated using the (modified) Schwartz formula (additional details in [section 5.2](#)). An unscheduled visit will be mapped to a scheduled visit per [section 2.10.2](#).

Potential Hy's Law events are defined as patients with concurrent occurrence of AST or ALT $> 3 \times ULN$ and TBIL $> 2 \times ULN$ and ALP $< 2 \times ULN$ in the same assessment sample during the on-treatment period. Potential Hy's law events will be tabulated using Safety set.

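### SAP 5.2 applies one Schwartz constant to every laboratory, although the protocol requires the modified Schwartz formula where creatinine is measured enzymatically; the change is not declared

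*SAP*

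**What the plan says.** **Protocol 7.2.2.5.2** has a two-branch rule. For local laboratories "where the enzymatic method is used to determine creatinine clearance the modified Schwartz formula will be used for analysis". For the others: "For calculated CrCl from local labs where Jaffe method is used we will use the Schwartz formula".

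**Protocol 10.5.3.3** refers to both formulas with one bracketed word and does not restate the split: "Creatinine clearance will be estimated using the (modified) Schwartz formula and the change from baseline will be provided".

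**SAP 2.1** says the data are analysed "according to the data analysis described in Section 10 of the ICL670F2429 protocol". **SAP 2.11.4** keeps the bracket and sends the reader on: "Creatinine clearance will be estimated using the (modified) Schwartz formula (additional details in" section 5.2.

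**SAP 5.2** opens with "The recalculated creatinine clearance will be calculated using the Schwartz formula (pediatric population at baseline"). It then prints clearance as k × height / (SCr × 0.01131) with two constants. One is 0.45, for children under 1 year, which cannot apply to this study's age range. The other is "k = 0.55 for children from 1 to 12 years based on current age". An MDRD equation is also printed, but only for the derived datasets.

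**SAP section 4** lists departures from the protocol on adverse-event summaries by chelation history, deaths, and ECG, auditory and ocular data. Creatinine clearance is not among them.

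**Protocol 5.3, exclusion 6** names a single formula: "Creatinine clearance using the Schwartz formula will be estimated from serum creatinine measured at each respective visit".

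**The concern.** The SAP section meant to supply the details supplies only the Jaffe branch. A programmer who follows SAP 5.2 departs from the protocol at every enzymatic-method laboratory. One who follows the protocol finds no modified formula to program, since neither document prints it.

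Absolute change in creatinine clearance is part of a secondary safety endpoint (Protocol Table 3-1, SAP Table 1-1). At enzymatic-method laboratories, three sets of results depend on the formula:

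- the baseline split at 90 mL/min in SAP 2.5;
- the notable (<60 mL/min) and extended (<40 mL/min) criteria in SAP Table 2-1;
- the summaries and box plots of change from baseline.

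The study is global and all specimens are analysed locally. The protocol provides for both assays, so the SAP cannot take the enzymatic share to be zero.

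**Working it through.** **Step 1: compare the rules.**

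| Place | Enzymatic laboratories | Jaffe laboratories |
|---|---|---|
| Protocol 7.2.2.5.2 | modified Schwartz | Schwartz |
| Protocol 10.5.3.3 and SAP 2.11.4 | both formulas implied by the bracket, no split stated | same |
| SAP 5.2 | Schwartz, k = 0.55 | Schwartz, k = 0.55 |
| Protocol 5.3, exclusion 6 (eligibility) | Schwartz | Schwartz |
| SAP section 4 | no change declared | no change declared |

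The protocol names two formulas for two assays, so one formula cannot serve both branches without a change to the protocol's rule.

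**Step 2: how the constant acts.** The SAP 5.2 formula is proportional to k. For a child 100 cm tall with serum creatinine 54.0 µmol/L, it gives 0.55 × 100 / (54.0 × 0.01131) = 55 / 0.6107 ≈ 90 mL/min.

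Assume the modified formula has the same form with constant k′, and let c = k′/0.55. Then:

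- SAP value / protocol value = 1/c.
- A SAP value falls below a threshold T only when the protocol value is below T × c.
- A protocol-formula change of −20 mL/min is reported as −20/c.

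**Step 3: range.** The documents do not give k′. The values of c below are assumptions, placed symmetrically because the sign is unknown.

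| c (assumed) | Ratio 1/c | SAP <90 means protocol value below | SAP <60 means below | SAP <40 means below | Change of −20 reported as |
|---|---|---|---|---|---|
| 0.75 | 1.333 | 67.5 | 45.0 | 30.0 | −26.7 |
| 0.90 | 1.111 | 81.0 | 54.0 | 36.0 | −22.2 |
| 1.00 | 1.000 | 90.0 | 60.0 | 40.0 | −20.0 |
| 1.10 | 0.909 | 99.0 | 66.0 | 44.0 | −18.2 |
| 1.25 | 0.800 | 112.5 | 75.0 | 50.0 | −16.0 |

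If k′ is below 0.55, the SAP counts fewer children under each threshold and reports larger absolute changes. If it is above 0.55, both reverse.

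**Step 4: dilution by the enzymatic share.** Let s be the share of patients at enzymatic-method laboratories, also not given. With equal mean protocol-formula clearance across laboratories, the shift in the pooled mean is s × (1/c − 1).

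| s | c = 0.75 | 0.90 | 1.00 | 1.10 | 1.25 |
|---|---|---|---|---|---|
| 0% | 0 | 0 | 0 | 0 | 0 |
| 50% | +16.7% | +5.6% | 0 | −4.5% | −10.0% |
| 100% | +33.3% | +11.1% | 0 | −9.1% | −20.0% |

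**Not affected:** the serum creatinine criterion in Table 2-1, percent change in clearance for a child measured by one assay throughout (which the SAP does not plan, since SAP 2.10.3 defines change as a difference), and the primary endpoint.

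**The case against.** The best counter-argument is that SAP 5.2 may be a deliberate single, standardised derivation. It labels the result recalculated clearance. It matches exclusion 6, which names Schwartz without a split. Protocol Section 10, which the SAP says it follows, does not state the assay rule; that rule sits in the visit-assessment section. This shows that the protocol is not uniform, but it does not remove the departure. Section 7.2.2.5.2 says expressly that its rule is for analysis, and both Section 10 and SAP 2.11.4 keep the bracketed word. If one formula was intended, it needed an entry in SAP section 4.

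A second argument is that no effect has been demonstrated. That stands as a limit on size. The constant, the form of the modified formula and the enzymatic share are all missing, and the effect may be nil. The ±25% range shows sensitivity only.

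A third is that exclusion 6 already bars clearance below 90 mL/min at screening. If sites applied Schwartz with k = 0.55, a SAP baseline below 90 would arise mainly from change between screening and day 1. So the single formula keeps the baseline table on the eligibility scale, and the two-formula option can create an apparent conflict with eligibility that has to be explained. This is a fair point about the baseline table. It does not touch the on-treatment criteria or the changes from baseline.

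Lastly, reach is limited. The study is single-arm and descriptive, and clearance is one of seven laboratory parameters in one secondary endpoint.

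**Conclusion.** The concern holds. SAP 5.2 states a rule that departs from Protocol 7.2.2.5.2 for enzymatic-method laboratories, it does not deliver what SAP 2.11.4 refers to it for, and the departure is undeclared. Confidence in the mismatch is high because it rests on the text alone.

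The numerical consequence is a scale factor of 0.55/k′ at the affected laboratories: 1.33, 1.00 or 0.80 for an assumed constant 25% below, equal to or 25% above 0.55. It rests on the modified formula having the same form. Its sign is unknown, and it vanishes if no laboratory uses the enzymatic method or if k′ = 0.55. This should be fixed before database lock. It does not threaten the primary result.

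**What to change.** Choose one of two routes.

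1. **Two formulas.** In SAP 5.2 print both formulas with their constants and select by each local laboratory's creatinine assay. The sponsor must supply the modified formula and constant. Cost: SAP wording, one programming branch and one assay field per laboratory, dated if a laboratory changes method during the study.
2. **One formula.** Declare and justify it in SAP section 4 as a departure from Protocol 7.2.2.5.2, and delete the bracketed word in SAP 2.11.4. Cost: two text edits and no new data.

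On either route, reconcile the formula named in exclusion 6 with Protocol 7.2.2.5.2 and 10.5.3.3, and footnote the baseline clearance table with the formula used for eligibility and the one used for analysis. Editing the protocol text itself would need an amendment under Protocol 12.1; the SAP edits and the footnote do not depend on it.

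The downside is that clearance-based counts may change. On route 1, a child not excluded under one formula may fall in the <90 mL/min baseline category under the other, which the footnote must explain. A sensitivity analysis with k = 0.55 throughout is optional.
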